- Ripple effects are unanticipated impacts to organizations or stakeholders that may result from evidence-based intervention implementation. A working group created a survey to measure the ripple effects of the program on practice staff and practice sites. The survey is adapted from a compilation of possible ripple effect categories identified and described in the literature (Pullmann et al 2022). It consists of 10 questions measuring potential unintentional impacts of the program on the delivery of other programs, job satisfaction, staff roles and relationships, accuracy of data, health equity, resources, delivery of health care, and culture. Questions will be answered on a 5-point bidirectional likert scale, with response options ranging from 'strong negative' to 'strong positive'. The survey will be administered to practice providers and staff at FGP practices at End of Study with the Exit Interviews and will follow the same protocol. Surveys will be sent via email and completed via REDCap. No identifying information will be collected. Risk to participants for completion of the survey is minimal with a slight risk to subject confidentiality. The deidentified data will be sent to the Research Coordinating Center and Data Safety Monitoring Board every September.
- Clinical Sustainability Assessment Tool - Clinical sustainability capacity is defined as the ability of an organization to maintain structured clinical care practices over time and to evolve and adapt these practices in response to new information. This tool 27-item tool is an assessment of current capacity for sustainability across a range of specific organizational and contextual factors. Responses will identify sustainability strengths and challenges that can be used to guide sustainability action planning for clinical practice.
- Exit Interview Guide for FGPs- to understand the satisfaction with the intervention and implementation at each site as well as areas for improvement

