ALTA is a health systems approach to improving medication adherence and BP control in primary care practices. It is designed to build practice capacity to address the needs of hypertensive patients by utilizing a team-based approach to delivering HTN care. ALTA includes five key components, which are conducted by existing members of the practice (Table 1): (1) Identify ALTA-eligible patients using hypertension registries. (2) Refer ALTA patients to a clinic Health Coach using the EHR. (3) Coach ALTA patients using a structured counseling tool integrated in the EHR to identify patients' treatment goals; assess their current level of BP control and medication adherence; identify barriers and facilitators to medication adherence; develop patient-centered adherence goals and action plans; and use a structured treatment algorithm to optimize patient antihypertensive medication regimen. (4) Document brief progress notes from the coaching session in the EHR to inform other team members of the patient's adherence status, action plans, progress toward goals, and any changes to the antihypertensive medication regimen. (5) Monitor and schedule follow-up sessions with ALTA patients in the EHR.

Table 1. ALTA components

ALTA components	ALTA Activities
Identify and Refer	
 • EHR registry to identify patients with uncontrolled HTN and non-adherent • EHR-based referral to MA/PCA/RN
Coach	
 • Structured assessment of medication adherence • Use of MINT to identify facilitators/barriers to adherence and discuss personalized strategies to improve adherence behaviors • Use of structured medication titration algorithm to optimize patient treatment regimen • Use of teach back to ensure patient understanding of treatment plan • Co-creation of culturally relevant goals and action plans
Document	
 • Structured documentation of coaching sessions in EHR to enable tracking patients' progress over time • EHR Documentation of individualized treatment plan, medication adherence goals, and action plan to guide future sessions and share with primary care provider for clinic visits
Monitor	
 • Consistent monitoring of patient progress through completion of and tracking follow-up sessions with ALTA patients

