5.3 Study Population

The study will be conducted in a network of 10 safety-net primary care practices in New York. The network of practices are recognized leaders in providing high quality, culturally responsive primary care and supportive services that ‘move the needle’ on health outcomes for low-income residents. Each year, the practices provide care to more than 125,000 patients generating over 800,000 annual visits in underserved communities around the metropolitan New York area. Sixty-eight percent of patients followed in the practices self-identify as Latino (English- or Spanish-speaking). Half of patients (53%) served at the practices have either Medicaid insurance or are uninsured.

Selection rationale: Despite over 30 years of medication adherence research with hypertensive patients, translation of this evidence into practice within safety-net settings has lagged considerably. Our study will contribute to the scientific knowledge about how efficacious implementation strategies such as PF may expedite the translation process for implementing evidence-based systems interventions into safety-net practices to reduce HTN disparities.

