Level of implementation adherence will be evaluated quantitatively as the degree to which the components of ALTA (e.g., identify, refer, coach, document, monitor) were implemented as intended, using data from checklists completed by the facilitators as well as extracted from the EHR. Each intervention component will be rated on a 3-point scale: 1=The component was not implemented, as per protocol; 2=The component was partially implemented; and 3=The component was fully implemented and/or modified with permission, as per protocol. We will calculate adherence as the number of components fully implemented (ratings of 3) divided by the total number of possible components (N=8). Practices will be considered adherent to the protocol if components were implemented completely and/or they were completed with an adaption that did not affect the programs core components and was approved by the study team. Facilitators will also complete monthly narrative reports that summarize all adaptations made to the components and what did/did not work for each practice context. We will also measure adherence through the Health Coaching Evaluation Checklist. The checklist will be used to count the parts of the standardized counseling script that were covered by the MAs at each health coaching session.

Implementation dose will be evaluated as the extent to which patients were exposed to ALTA. We will collect data on utilization patterns of the different ALTA components including the mean number of: ALTA-eligible patients identified in the registry and referred to a Health Coach; health coaching sessions completed with ALTA patients; entries in the EHR-embedded coaching script; progress notes documented in the EHR and shared with the care team; and follow-up sessions that are scheduled and/or completed. System files will be extracted quarterly and will contain date and time stamps as well as user logins for the tools used.

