Level of implementation adherence will be evaluated quantitatively as the degree to which the components of ALTA (e.g., identify, refer, coach, document, monitor) were implemented as intended, using data from checklists completed by the facilitators as well as extracted from the EHR. Each intervention component will be rated on a 3-point scale: 1=The component was not implemented, as per protocol; 2=The component was partially implemented; and 3=The component was fully implemented and/or modified with permission, as per protocol. We will calculate adherence as the number of components fully implemented (ratings of 3) divided by the total number of possible components ($N=8$). Practices will be considered adherent to the protocol if components were implemented completely and/or they were completed with an adaption that did not affect the programs core components and was approved by the study team. Facilitators will also complete monthly narrative reports that summarize all adaptations made to the components and what did/did not work for each practice context. We will also measure adherence through the Health Coaching Evaluation Checklist. The checklist will be used to count the parts of the standardized counseling script that were covered by the MAs at each health coaching session.

Part 2.

- Level of Implementation dose will be evaluated as the extent to which patients were exposed to ALTA. We will collect data on utilization patterns of the different ALTA components including the mean number of: ALTA-eligible patients identified in the registry and referred to a Health Coach; health coaching sessions completed with ALTA patients; entries in the EHR-embedded coaching script; progress notes

documented in the EHR and shared with the care team; and follow-up sessions that are scheduled and/or completed. System files will be extracted quarterly and will contain date and time stamps as well as user logins for the tools used. We will also calculate the average program dose, which is defined as all the number of times the MA-led health coaching sessions occurred during the implementation phase divided by the total number of patient encounters at the clinic during that same period of time (i.e., 12 months). To compare average dose across the practices, we will use a least square means analysis of variance (ANOVA) model with weighting by the number of patients seen in each practice within the specified time period.

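### The adherence score divides by eight components where the plan defines five, and the average-dose ratio divides coaching sessions by all clinic encounters

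*Combined protocol and SAP*

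**What the plan says.** **Adherence.** Section 3.2 states "ALTA includes five key components" and numbers them: identify, refer, coach, document, monitor. Table 1 in that section arranges them in four rows, with identify and refer sharing one, and lists ten activities. Section 6.1.4 rates each component from 1 (not implemented) to 3 (fully implemented, or modified with permission) and then gives the score: "We will calculate adherence as the number of components fully implemented (ratings of 3) divided by the total number of possible components (N=8". Section 6.4.3.1 repeats the rule, "the number of components fully implemented (ratings of 3) divided by the total number of possible components", again with N=8. Just before the formula, both sections name the same five components, as examples. Neither lists eight.

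**Dose.** Both sections describe dose as how far patients were exposed to ALTA. Both plan mean counts of patients identified and referred, coaching sessions, script entries, progress notes and follow-up sessions. Only section 6.4.3.1 adds an average program dose: MA-led coaching sessions in the implementation phase "divided by the total number of patient encounters at the clinic during that same period of time", that is, 12 months. Practices are then compared on average dose by an ANOVA weighted by the number of patients seen.

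**Use.** Adherence and dose are two of the five fidelity domains. Section 6.4.3.1 combines the domains into a composite that is used to predict change in BP control and medication adherence.

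**The concern.** A proportion can be interpreted only if its denominator is the number of things that could have counted in its numerator. For adherence the plan gives one number for that set in section 3.2 and another in the formula, so the score cannot be computed from the document without guessing what is rated. A practice that delivers every named component could be reported as only partly adherent.

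For dose, the denominator includes patients who are outside the program by design. The quantity compared across practices then does not answer the stated question about patient exposure. Both scores belong to the primary outcome and feed the composite, so these ambiguities carry into the main fidelity result and its planned link to clinical outcomes.

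**Working it through.** **1. Can 8 be reproduced?**

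The inputs are N=8 (sections 6.1.4 and 6.4.3.1), five components (section 3.2), and Table 1 with rows Identify and Refer (2 activities), Coach (5), Document (2) and Monitor (1).

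| Count | Items | Equals 8? |
|---|---|---|
| Components named in the text | 5 | No |
| Table 1 rows | 4 | No |
| Table 1 activities, 2+5+2+1 | 10 | No |

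Mixed counts are also possible, with each row either collapsed to one item or expanded into its activities. The eight combinations sum to 4, 5, 5, 6, 8, 9, 9 and 10. Only one gives 8: Identify-and-Refer 1 + Coach 5 + Document 1 + Monitor 1. It needs identify and refer to be merged, although section 3.2 numbers them separately, and the plan nowhere states it.

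**2. What follows if five components are rated?**

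Score = (number rated 3)/8. The attainable values are 0, 12.5, 25, 37.5, 50 and 62.5%. With a denominator of 5 they are 0, 20, 40, 60, 80 and 100%. Full implementation is 5/8 = 62.5% as written and 5/5 = 100% with the matching denominator.

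**3. Does the item set matter beyond scale?**

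Take two hypothetical practices. A fully delivers all coaching activities and nothing else. B delivers everything except coaching.

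- Five components, denominator 5: A = 1/5 = 20%, B = 4/5 = 80%.
- The mixed eight items, denominator 8: A = 5/8 = 62.5%, B = 3/8 = 37.5%.

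The order reverses, so the choice of rated items can change which practice looks more adherent.

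**4. The dose ratio.**

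Let N be a practice's patients, e the share eligible for ALTA, s the sessions per eligible patient and V all encounters in 12 months.

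Dose ratio = e × N × s / V

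Section 5.3 gives more than 125,000 patients a year, "generating over 800,000 annual visits", over 10 practices. An even split is an assumption. It gives N = 125,000/10 = 12,500 and V = 800,000/10 = 80,000. The documents do not give e or s, so the values below are also assumptions.

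- e = 1%, s = 4: 0.01 × 12,500 × 4 / 80,000 = 500/80,000 = 0.625%.
- e = 5%, s = 4: 0.05 × 12,500 × 4 / 80,000 = 2,500/80,000 = 3.125%.

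Sessions per eligible patient are 4 in both cases, yet the ratios differ fivefold, exactly as the eligible shares do.

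For the general level, assume 70 coached patients in a practice. One session each gives 70/80,000 = 0.09%, and 12 sessions each give 840/80,000 = 1.05%.

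**The case against.** **On adherence.** The five names are introduced as examples. Section 6.1.4 also says the domains are scored with a structured tool built for this study, which the document does not reproduce. That tool could have eight items. A reader might infer that 8 is simply wrong and that the denominator must be 5. The documents do not show this, and if eight items are rated, dividing by 5 would allow 8/5 = 160%. This part of the objection stands and makes the 62.5% conditional. It does not remove the contradiction, because the examples reproduce section 3.2's complete numbered list and no eight-item list is given.

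A reader might also infer that overall fidelity is capped at 62.5%. Adherence is one of five domains, the composite is built from a joint display that favors the qualitative data where sources diverge, and no numeric weights or adherence cutoff are stated. If the same five items are rated everywhere, 8 in place of 5 multiplies every score by 5/8 and leaves rankings and tests on that score unchanged. Nor do the documents support scores of 10/8 = 125%: Table 1 distinguishes components from activities, and the formula counts components.

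**On dose.** The ratio is one of several dose measures, and the mean counts already focus on ALTA patients. Sessions per clinic encounter can be read as the reach of what section 6.3.4 describes as a clinic-wide initiative. It is a question of validity, not an arithmetic error. All of that stands. But the ratio is labeled average dose, and it is the only dose measure given a specified comparison between practices. The other counts do not correct that comparison.

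**Conclusion.** The concern holds in two limited forms.

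**Adherence:** the plan contradicts its own component count within a primary-outcome domain, and the set of rated items is undefined. Full implementation scores 62.5% if the five named components are rated and 100% if an unprinted list of eight is rated. The document does not say which applies.

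**Dose:** with equal coaching per eligible patient, the ratio scales with the eligible share of the practice, so the ANOVA can show practice differences that are not differences in delivery. The fivefold example rests on assumed shares of 1% and 5%, 4 sessions per patient and an even split of network volume. The direction of the problem does not depend on those values, but its actual size cannot be stated from the documents.

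The power calculation in section 6.4.2 concerns BP control and is unaffected.

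**What to change.** **Adherence.** List the items actually rated on the facilitator tool and set the denominator equal to their number, consistently in sections 3.2, 6.1.4 and 6.4.3.1. Use 5 if the five named components are rated, and 8 only if eight listed items are rated. Rescore completed checklists if the denominator changes.

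**Dose.** Define average program dose as coaching sessions per ALTA-eligible patient, or per encounter of ALTA-eligible patients, with eligibility taken from the EHR registry. Use that measure in the between-practice ANOVA, with weights that match its denominator. The all-encounter ratio may be kept as a descriptive measure of reach.

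**Cost.** Short text changes in three sections, a small amount of additional EHR extraction, and possibly rescoring. Section 6.1.4 already plans registry counts of eligible patients and reports of eligible patients who were not enrolled, so no new data collection from patients or staff should be needed.

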5.3.2 Eligibility Criteria/Vulnerable Populations

The study population will include practice clinical and nonclinical NYULH staff and patients with uncontrolled HTN receiving care in the network of 10 safety-net practices in New York.

Patient Eligibility Criteria

Inclusion Criteria:

- Be fluent in English or Spanish
- Be age 18 years or older
- Receiving care at one of the 10 practices
- Have uncontrolled HTN documented in the EHR on at least two visits in the past year (defined as an average BP \geq 140/90 mmHg)
- Have been prescribed at least one anti-hypertensive medication and be non-adherent to their medications, defined as adherence $<80\%$ in the preceding 12 months, as determined by prescription orders obtained from the clinic EHR.

Exclusion Criteria:

- Being deemed unable to comply with the study protocol (either self-selected or by indicating during screening that s/he could not complete all requested tasks)
- Participation in other hypertension-related clinical trials
- Have significant psychiatric comorbidity or reports of substance abuse (as documented in the EHR)
- Plan to discontinue care at the practice within the next 15 months

Clinic and nonclinical staff Eligibility Criteria

Inclusion criteria:

- Primary care provider (MD/DO, NP), Nurse, Medical Assistant, or administrative staff employed at the participating practices and interacts with at least five patients with a diagnosis of HTN.

Exclusion criteria:

- Refuse to participate.

Control group eligibility criteria

Inclusion criteria:

- Patients who fit the inclusion criteria of the intervention group

Exclusion criteria:

- The same exclusion criteria of the intervention group will be applied to the control group
- Patients who refuse to participate in the evaluation

As ALTA grows and becomes standard-of-care, we anticipate that some patients may crossover from the control group to intervention group. The opposite will not occur because that is considered a withdrawal from the study. Our sample size for the control group can remain dynamic in that fashion, and we will recruit until the end of the evaluation period.

Vulnerable Populations

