Medication adherence will be assessed via pharmacy refills obtained from prescription orders in the clinic EHR using the proportion of days covered (PDC) metric. The PDC is calculated as the total number of days covered by the medication divided by the number of days between the first fill of the medication in the study period and the end of the study period. Thus, as opposed to other pharmacy refill metrics, the PDC accounts for non-persistence with medications by tracking medications during the study period despite early discontinuation. We will count the days the patient was covered by each of their prescribed antihypertensive medications based on the prescription fill date and days of supply. If prescription fills for the same medication overlap, then we will adjust the prescription start date to be the day after the previous fill has ended. Patients will be considered adherent if they fill $\geq 80\%$ of their antihypertensive medications over the 12 months.

Tertiary Outcomes

Relationship commitment: To assess patients' *perceived commitment* to their PCP, we will utilize the self-report measure developed by Berry et al. in a sample of primary care patients. The 5-item measure asks patients to rate their degree of commitment to the relationship with their doctor on a 7-point Likert scale (*strongly disagree* to *strongly agree*). Sample items include: *The relationship with my doctor is...something I am committed to; something I care about; and important to me.* This measure will be administered to patients at baseline and 12 months.

To assess the *behavioral and affective indicators* of relationship commitment we will use NLP and analyze text of patient-provider interactions that

Part of the clinical interaction	Examples of relationship commitment behaviors and affect	Measurement strategy
Initiating the session	Patient and PCP creates a warm and friendly environment; collaboratively identify reason for visit and negotiate agenda	Sentiment analysis to identify affective behaviors (warmth, cheerfulness, and attentiveness) ¹⁰⁸

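### PDC is counted from each drug's first fill, so uncovered days before that fill are lost, a patient with no fill has no score, and no patient-level rule is stated

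*Combined protocol and SAP*

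**What the plan says.** Sections 5.2.2 and 6.1.4 give the same definition of PDC.

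- **Denominator.** Covered days are "divided by the number of days between the first fill of the medication in the study period and the end of the study period".
- **Numerator.** Covered days are counted separately for every antihypertensive a patient has been prescribed, from fill dates and the length of each supply.
- **Stopped drugs.** The stated merit of the metric is that "the PDC accounts for non-persistence with medications by tracking medications during the study period despite early discontinuation".
- **Overlap.** When one refill is collected before the last has run out, the later one is moved to start once the earlier one is used up. This covers refills of the same drug only.
- **Adherent.** "Patients will be considered adherent if they fill" at least 80% "of their antihypertensive medications over the 12 months". Section 6.2.1 also describes PDC as a measure over 12 months.

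Three other places bear on this. Section 5.3.2 requires patients to "Have been prescribed at least one anti-hypertensive medication and be non-adherent to their medications", meaning below 80% in the preceding 12 months. Table 1 in section 3.2 lists as an ALTA activity "Use of structured medication titration algorithm to optimize patient treatment regimen". Section 6.4.3.2 models PDC from the pharmacy records that are available, using models similar to those for BP control. Its rule that a missing follow-up value counts as failure is stated for BP only.

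**The concern.** A clock that starts at the first fill can suit people starting a drug. These patients are not starting: they are already prescribed treatment when the period opens, and were selected for poor coverage. Months without a fill are what coaching is meant to change, but under the written formula those months enter neither numerator nor denominator. At the extreme, a patient who fills nothing has no first fill, so the ratio does not exist.

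Section 6.2.1 assesses efficacy through BP control and this metric. Adherence also enters the fidelity-association analysis (section 6.4.3.1) and a tertiary objective (section 4.4). If late filling, non-filling or drug replacement differs between usual care and implementation, the PDC contrast partly reflects the scoring rule. Several choices are also open, so two analysts could compute different outcomes from the same records.

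**Working it through.** The documents give no expected PDC, standard deviation or power for this outcome (section 6.4.2 is based on BP control), so there is no planned figure to reproduce. The check applies the written formula to worked cases. The 365-day period, supply lengths, fill days and switch days are assumptions.

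**1. Late first fill.** Let f be the days elapsed before the first fill and C the days covered after it.

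- Written PDC = C / (365 − f)
- Fixed-window PDC = C / 365, with no supply carried in

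| Supply | f | Written PDC | Fixed-window PDC |
|---|---|---|---|
| 90 days | 180 | 90/185 = 48.6% | 90/365 = 24.7% |
| 90 days | 253 | 90/112 = 80.4% | 24.7% |
| 90 days | 275 | 90/90 = 100% | 24.7% |
| 60 days | 290 | 60/75 = 80.0% | 60/365 = 16.4% |
| 30 days | 328 | 30/37 = 81.1% | 30/365 = 8.2% |

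The values f = 253, 290 and 328 are the earliest at which a single supply of that length reaches 80%. Carry-over does not rescue the score: with a full 90-day supply in hand on day 1, the late 90-day filler reaches (90 + 90)/365 = 49.3% and the late 30-day filler (90 + 30)/365 = 32.9%. A patient fully covered from the first fill onward scores 100% as written but falls below 80% of the year once f exceeds 0.2 × 365 = 73.

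**2. The score can move against coverage.** One 90-day supply from f = 270 gives 90/95 = 94.7% as written and 24.7% of the year. In contrast, 220 days of supply from f = 90 gives 220/275 = 80.0% as written and 220/365 = 60.3% of the year. Moving from the first pattern to the second raises coverage by 35.6 points and lowers the written score by 14.7. The reverse move does the opposite.

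**3. No fill.** With no first fill the ratio is undefined; on a fixed window it is 0/365 = 0%. As an illustration only, assume fillers average 0.65 in both phases and 5% to 15% of patients have no fill. With zeros counted, the mean is 0.65 × 0.95 = 0.6175 to 0.65 × 0.85 = 0.5525. If the no-fill share falls from 15% to 5% between phases, mean coverage rises by 0.065; if it rises from 5% to 15%, it falls by 0.065. Among patients with a defined PDC the difference is zero both times. For scale, section 3.1 reports a 6-point adherence difference (78% vs 72%) in the predecessor trial, without naming the metric.

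**4. Drug replaced with no gap.** Drug A gives way to drug B on day 180 and every day is covered. Drug A scores 180/365 = 49.3% and drug B 185/185 = 100%. No cross-drug rule is stated, so five were tried.

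| Rule | No other drug | Two other fully covered drugs |
|---|---|---|
| Mean of drug PDCs | 74.7% | 87.3% |
| Pooled days | 365/550 = 66.4% | 1095/1280 = 85.5% |
| Every drug at least 80% | fails (A = 49.3%) | fails |
| Share of drugs with PDC at least 80% | 1 of 2 = 50% | 3 of 4 = 75% |
| Any antihypertensive covers the day | 100% | 100% |

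The day matters too. With no other drug, the patient is classed adherent from day 219 (mean), 274 (pooled) or 292 (every drug, or share). The same history can therefore be adherent or not, depending on a rule the plan does not contain.

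**The case against.** The late-fill cases are at the edge: a patient must be at least 80% covered after the first fill, and one 90-day supply at f = 180 scores only 48.6%. The references to 12 months may mean that a fixed window was intended. Mixed models keep a patient who has PDC in one period, and section 6.4.3.2 plans missing-at-random sensitivity analyses and a comparison of patients with and without missing values. Read literally as a share of medications filled, the adherent rule scores a never-filler 0% and a switched patient 2 of 2. Adherence is secondary, power rests on BP control, and a self-report adherence survey is also planned.

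Much of this stands, and it limits the point. A reader might infer that switched patients are scored non-adherent in general. The documents do not support that: the result depends on the switch day, the other drugs and an unstated rule. Nor do they show that switching is more common under ALTA. Titration and the dose changes recorded at 12 months (section 6.1.4) need not replace a drug, and no switch rate is given.

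It does not remove the core. The formula is stated twice and starts at the first fill; the 12-month wording makes the text inconsistent without replacing the formula. A PDC missing because nothing was filled is missing because of its own value, which a missing-at-random model does not repair. The literal adherent rule settles only the binary classification, and by a quantity other than PDC.

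**Conclusion.** The point holds as a should-fix. Followed as written, the formula can score a late filler at 80% or more with about 25% (90-day supply) or 8% (30-day supply) of the year covered, provided coverage after that fill is good, and it leaves a never-filler without a value. The percentages rest on an assumed 365-day period with no carried-over supply. The window, the adherent rule, the cross-drug rule and the handling of a clinic-directed stop or switch are also inconsistent or absent.

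A reader might go further and infer that the effect of practice facilitation on PDC is biased, or biased in a known direction. The documents do not support that. They give no rates of late filling, non-filling or switching in either phase, so bias is possible but its sign and size cannot be determined. Nor do never-fillers look adherent; they have no PDC. Because the outcome is secondary and the sample size does not depend on it, this falls short of a must-fix.

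**What to change.** In sections 5.2.2 and 6.1.4, before PDC is analysed:

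- Use one fixed observation window of the same length in both phases. The length of the pre-intervention PDC window is not stated, while section 5.1.1 gives usual care as the first 3 months.
- For drugs already prescribed when the period starts, begin the denominator on day 1 and count carry-over supply. For drugs first prescribed within the period, begin at the prescription date.
- Set PDC = 0 when there is an active prescription and no fill.
- State one patient-level cross-drug rule, for example day-level coverage by any currently prescribed antihypertensive. Alternatively, end a drug's denominator at a documented stop or switch, where that date can be extracted.
- Define adherent as patient-level PDC of at least 80%.
- Report the first-fill PDC as a sensitivity analysis.

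The cost is wording plus some reprogramming. The workbench report in section 6.1.4 already includes PDC scores and the medication list, but carry-over needs fills from before the period. The documents do not confirm that stop dates can be extracted; the day-level rule relies on them less. Refills are taken from prescription orders, so it should be confirmed that the extract separates an order from a fill. Reported PDC will be lower.
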